9. COMPENSATION

Will participants be compensated for participation?

Yes

If so, please include details.

Compensation has been set to be commensurate with previous studies with these populations in Kuala Lumpur, Malaysia.

Phase 1: *Participants who complete the study in person will be compensated 50RM/hour, which is approximately \$11.60. Participants will be compensated for their time during the two workshops. As noted in the consent form, participants who do not complete the study will receive pro-rated compensation. Participants who complete the study online will be*

compensated 50RM/submission (responding to each submission is expected to take approximately one hour). Participants will also be compensated for their time completing the consent process and watching the introductory videos, as well as completing a survey regarding their experiences completing the study online (25 RM/activity because each activity is expected to take approximately one-half hour).

Phases 2-4: *Doctors will be compensated 75RM/hour of study participation, which is approximately \$17.40. Participants of Phase 2 will be compensated 1 hour per day for responding to online focus group questions, for up to 3 days of participation (maximum = 225RM). Participants of Phase 3 will be compensated for their time spent completing pre-test trainings and engaging in the qualitative interview, for up to 9 hours of compensation (maximum = 675RM). Participants of Phase 4 will be compensated for their time completing surveys, for up to three hours of compensation (maximum = 225RM). Participants invited to complete focus groups will also be compensated for their time (75RM). As noted in the consent forms, participants who do not complete the studies will receive pro-rated compensation. Participants of Phase 4 will also be given lunch vouchers on days when they participate (30RM or about \$7).*

The compensation schedule is set differently for Phases 3 versus 4 participants because Phase 3 participants are expected to receive less benefit from their engagement in the study. Participants in Phase 3 will receive very limited training in HIV testing, prevention, and linkage to care that is unlikely to address many of their training needs. Participants in Phase 4 will receive a much more comprehensive training program covering these areas that is likely to address most of their training needs, and also may be eligible to receive Continuing Medical Education credits.

10. DATA

Will subjects be anonymous to the researcher?

No.

If subjects are identifiable, will their identities be kept confidential? (If yes, please specify how)

Phase 1: *No identifying information will be collected from participants.*

Phases 2-4: *Clinicians will be given an alphanumeric participant ID code. All participant data (e.g., survey results) will be stored along with this participant ID, rather than participants' names. The log linking participant IDs with participant names will be stored on a password-protected server with access restricted to members of the study team during the duration of the study. After the study, the log will be destroyed so that there is no record linking participants with their data.*

Results from all studies will be reported in aggregate.

How will data be stored and kept secure (specify data storage plans for both paper and electronic files. For guidance see <http://www.udel.edu/research/preparing/datasstorage.html>)

Paper files will not be collected.

All digital files, including audio files and transcripts, will be stored on password protected files on UD maintained servers with regular and secured back-up. Data will be collected using UD applications (e.g., Qualtrics and HIPAA-compliant Zoom).

Additionally to keep photo data secure, a HIPPA-compliant website has been created for the study. Photos taken on cell phones will be uploaded through the website. Photos and captions written by participants will be encrypted both at rest and in transit.

How long will data be stored?

Coded data will be stored indefinitely.

Will data be destroyed? YES NO (if yes, please specify how the data will be destroyed)

After the study, the log linking participant IDs with participant names will be permanently deleted so that there is no record linking participants with their data.

Will the data be shared with anyone outside of the research team? YES NO (if yes, please list the person(s), organization(s) and/or institution(s) and specify plans for secure data transfer)

How will data be analyzed and reported?

Phase 1: *Following standard qualitative data analysis methods, we will review all of the final presentations, explore repetitions across presentations to identify themes, and then develop a codebook listing themes with a detailed description, inclusion/exclusion criteria, and examples. We will upload the final presentations, story scripts, and photographs into Dedoose (a qualitative coding software system that facilitates collaboration between coders, and can be used to analyze text, photograph, and video data). Two coders will review videos, and then mark areas of text and photographs pertaining to themes. They will practice with a random sample of 20% of data, coding independently and reviewing together. We will clarify ambiguity in the codebook by adding examples. Training will continue until coders consistently identify and mark each theme. Coders will then work on each interview independently, after which we will measure coder consistency, evidenced by Kappas of ≥ 0.70 . We will use Dedoose to examine the distribution of themes. Results are expected to provide evidence regarding stigma perceived by participants from clinicians.*

Phase 2: *We will apply the same analytic steps and use the same software to analyze the focus group data as those that we will apply to the Photovoice data (Phase 1), except that our analysis will concentrate on focus group transcripts. Results are expected to provide evidence regarding clinician perspectives on stigma in healthcare settings, and insight into the context for intervention delivery.*

Phase 3: *We will apply the same analytic steps and use the same software to analyze the interview data as those that we will apply to the Photovoice and focus group data (Phases 1-2), except that our analysis will concentrate on interview transcripts. All qualitative interviews will be transcribed by our trained research assistants. Results are expected to provide insight into aspects of the intervention that we may need to change before implementing it in Phase 4.*

Phase 4: *Quantitative analyses will be conducted in R version 3.6.2 and include an examination of descriptive statistics and generalized linear models. We will examine changes in mean self-reported stigma (i.e., prejudice, stereotypes, and discrimination) across the 3 time-points of data collection. We will use a two-way repeated measures ANOVA to determine whether any change in stigma is associated with the interaction between the type of condition (factor one) and time (factor two). Qualitative analyses will follow the same*

analytic steps and use the same software as those that we will apply Phases 1-3, except that our analysis will focus on interview transcripts. All qualitative focus groups will be transcribed by our trained research assistants. Results are expected to provide insight into the acceptability and feasibility of the intervention, including barriers to and facilitators of implementation and reasons for withdrawal, as well as participants' perceptions of impact on stigma and care delivery.

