5. RESEARCH ABSTRACT

Please provide a brief description in LAY language (understandable to an 8th grade student) of the aims of this project.

Clinicians who stigmatize people at risk of or living with HIV provide worse HIV testing, treatment, and linkage to care services to these populations. To date, the vast majority of stigma-reduction interventions for clinicians have occurred in single healthcare facilities. We propose to deliver evidence-based stigma reduction tools through a popular teletraining platform for clinicians, Project ECHO[®]. Project ECHO[®] (Extension for Community Healthcare Outcomes) has trained, supported, and empowered 70,000+ clinicians to provide a wide range of specialty care services in 37+ countries globally, including HIV testing, prevention, and linkage to care. It uses a "hub and spoke" model wherein non-specialists in community setting "spokes" learn from and collaborate with specialists at academic "hubs" via

videoconferencing technology (i.e., Zoom software). By delivering stigma-reduction tools through Project ECHO®, we could substantially extend the reach of stigma-reduction interventions for clinicians.

There are four phases of our project:

- **Phase 1:** We will explore experiences of stigma among people at risk of and living with HIV using Photovoice, a qualitative data collection technique involving photography and story-telling (n=35).
- **Phase 2:** We will explore clinicians' perspectives on an intervention to address stigma through online focus groups (n=40).
- **Phase 3:** We will conduct a brief pre-test of our intervention protocol with a small sample of clinicians (n=5).
- **Phase 4:** We will pilot test our intervention protocol among clinicians, comparing it to two control conditions (n=78). Our intervention materials will include Photovoice presentations created by participants in Phase 1 of the study. Importantly, these presentations will be screened to ensure that they do not contain identifying information (e.g., faces).

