Phases 2-3: We plan to recruit clinicians by emailing information about the study to members of the Malaysian Medical Association and via established informal networks on social media such as DOBBS (Doctors Only Bulletin Board System) and the Malaysian Primary Care Network. To date, we have had success recruiting Malaysian clinicians via email (participation ranging from 33.4-39.6% of clinicians contacted via email).

Phase 4: We will recruit clinicians from the memberships of the Malaysian Medical Association, Family Medicine Association of Malaysia (FMSA), and Malaysian Primary Care Network. The organizations will share an advertisement to their social media site, which will direct participants to Qualtrics. Participants will be given more information about the study and consent to completing a brief survey and being assigned to a study condition (i.e., step 1 consent). They will then be randomly assigned to a study condition. Clinicians' previous experience with HIV testing will be taken into account in the randomization process to ensure equal distribution of previous experience among study conditions. Once they have been assigned, we will contact them again, provide additional information about their condition, and consent them to the full study (i.e., step 2 consent).

Describe what exclusionary criteria, if any will be applied.

Clinicians who participate in the Phase 3 pre-test will not be eligible to participate in the Phase 4 pilot test.

Describe what (if any) conditions will result in PI termination of subject participation.

N/A

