Phases 2-4: To protect clinicians from discomfort, we will emphasize during the informed consent process that they may choose to not engage in conversations that make them uncomfortable, skip survey and/or interview questions, and end the study at any time. To protect clinicians from a breach of confidentiality, we will store all electronic data on a password-protected server with access restricted to members of the study team. Clinicians will be given an alphanumeric participant ID code. All participant data (e.g., survey results) will be stored along with this participant ID, rather than participants' names. The log linking participant IDs with participant names will be stored on a password-protected server with access restricted to members of the study team during the duration of the study. After the study, the log will be destroyed so that there is no record linking participants with their data. Additionally, we will use a HIPAA compliant version of zoom when conducting interviews and focus groups with clinicians. Additionally, participants of the online focus groups (Phase 2) will be able to use a pseudonym instead of the real name while responding to questions.

Nettrour J. F., Burch, M. B., & Bal, B. S. (2019). Patients, pictures, and privacy: Managing clinical photographs in the smartphone era. *Anthroplasty Today*, 57-60.

Describe any potential direct benefits to participants.

Phase 1: Participants may enjoy the opportunity to learn about photography or find the opportunity to document and share their experiences via Photovoice to be fulfilling.

Community groups in which participants are involved may use the Photovoice presentations for advocacy purposes, which could lead to policy changes that benefit the populations that participants represent. Yet, participants are unlikely to personally benefit from participation in this phase.

Phase 2: *Participants may find the opportunity to provide feedback on the intervention to be fulfilling. Yet, participants are unlikely to personally benefit from participation in this phase.*

Phase 3: *Participants may benefit by receiving some limited specialty training in HIV testing, prevention, and linkage to care.*

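### The Phase 4 stigma outcome is tested by repeated measures ANOVA with no missing-data method, so clinicians missing one survey may be dropped, losing precision and possibly biasing the arm comparison

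*Combined protocol and SAP*

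**What the plan says.** The Phase 4 quantitative plan is one short paragraph in section 10 (DATA). The analyses "include an examination of descriptive statistics and generalized linear models". Mean self-reported stigma is to be followed "across the 3 time-points of data collection", and the only test named for it is this: "We will use a two-way repeated measures ANOVA to determine whether any change in stigma is associated with the interaction" of condition with time. Section 6 gives three arms of 26 and a programme of 9 months.

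The document expects incomplete participation in several places:

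- Section 8 tells clinicians in Phases 2-4 that they may "skip survey and/or interview questions, and end the study at any time".
- Section 9 notes that "participants who do not complete the studies will receive pro-rated compensation".
- Section 7 describes two-step consent for Phase 4: "Once they have been assigned, we will contact them again, provide additional information about their condition, and consent them to the full study". Clinicians can therefore leave after learning their arm.
- Section 10 lists among the qualitative topics "barriers to and facilitators of implementation and reasons for withdrawal".

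No section gives an analysis set, an expected attrition rate, a missing-data method or a sensitivity analysis.

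**The concern.** In its usual wide-format form, a repeated measures ANOVA needs all three scores from each clinician. One missed survey removes that clinician's other surveys too. A long-format fit in R with a clinician error term keeps partial records, but with incomplete data it divides the condition-by-time information between two error strata and reports two tests. The plan does not say which form is meant, so both the analysed population and the test remain open until the data are seen. The mention of generalized linear models does not settle this, because nothing is said about how they would treat repeated or incomplete measurements.

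Two things are at stake. With 26 per arm, surveys already collected and paid for would be thrown away. The completer comparison can also be biased if missingness depends on stigma and does so differently by arm. That is plausible, since the two Project ECHO arms differ in stigma content and full consent follows assignment, but the document does not establish it.

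**Working it through.** **Inputs from the document.** 3 arms × 26 = 78, which agrees with section 5; three surveys. No attrition rate, SD or within-person correlation is stated, and there is no power calculation to reproduce.

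**Assumptions.** Baseline complete; a fraction m = 10%, 15% or 20% missing at each of two follow-ups; SD = 1; equal correlation ρ = 0.5 (range 0.4 to 0.7). Two patterns are used: independent misses, and monotone dropout (once gone, gone). Both give the same completer fraction.

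**Completers.** The fraction is (1−m)² = 0.81 / 0.7225 / 0.64.

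- Per arm: 26 × fraction = 21.1 / 18.8 / 16.6.
- Excluded overall: 78 × (1 − fraction) = 14.8 / 21.6 / 28.1.

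**Observed surveys discarded.** This is 1 − 3(1−m)² / (expected surveys per clinician).

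- Independent: the denominator is 1 + 2(1−m) = 2.8 / 2.7 / 2.6, giving 13 / 20 / 26%.
- Monotone: the denominator is 1 + (1−m) + (1−m)² = 2.71 / 2.5725 / 2.44, giving 10 / 16 / 21%.

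**Precision of the arm 3 versus arm 2 difference in baseline-to-final change.** With n per arm, SE = √[2 × 2(1−ρ)/n]. With no missing data this is √(2/26) = 0.28 SD. For completers it is √(2/21.06), √(2/18.785) and √(2/16.64). For the mixed model, the expected information is summed over missing-data patterns (26 × pattern probability × inverse covariance of the surveys observed), inverted, and applied to the contrast (−1, 0, 1).

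| Missing per follow-up | Completers | Mixed model, independent | Completer excess | Mixed model, monotone | Completer excess |
|---|---|---|---|---|---|
| 10% | 0.308 | 0.288 | 7% | 0.299 | 3% |
| 15% | 0.326 | 0.293 | 11% | 0.313 | 4% |
| 20% | 0.347 | 0.300 | 15% | 0.328 | 6% |

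For ρ from 0.7 down to 0.4, the monotone excess is 2-3 / 3-5 / 4-7%.

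**Bias.** 1.5 million clinicians were simulated per scenario, with true effect zero, ρ = 0.5, and monotone dropout depending on the last observed score in one arm only. The completer contrast is off by:

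- 0.032 / 0.047 / 0.061 SD when the odds of dropout double per SD;
- 0.048 / 0.067 / 0.087 SD when they triple.

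The likelihood estimate is within about 0.001 SD of zero. If both arms share the mechanism, the completer bias is about zero. Against the completer standard error, the range runs from 0.032/0.308 = 0.10 to 0.087/0.347 = 0.25.

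The figure depends on the mechanism. Suppose dropout occurs only after survey 2 and depends on that score in one arm. With equal correlations, the baseline-to-final completer bias is about zero. With correlations of 0.5 (surveys 1-2), 0.7 (2-3) and 0.4 (1-3), it is −0.04 / −0.05 / −0.07 SD at roughly 10 / 20 / 30% dropout, against −0.007 to 0.000 using all observed surveys. The direction is therefore not fixed either.

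**Software behaviour.** One dataset of 78 clinicians with 15% monotone loss per follow-up was simulated and fitted in R 4.3.3.

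- The wide-format fit kept 58 clinicians. It used 58 × 3 = 174 of 204 observed surveys and discarded 30.
- The long-format fit with a clinician error term kept all 78 but gave two condition-by-time tests, F(4,69) = 0.39 and F(4,120) = 1.93.
- A REML model with unstructured covariance used all 204 surveys in one test.

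**The case against.** The best counter-argument is that the avoidable harm is small. Withdrawal produces mostly monotone loss, where analysing completers costs only 3 to 6% in standard error. Most of the rise from 0.28 to 0.31-0.35 SD reflects data never collected, which no model recovers. The bias needs dropout that follows stigma in one arm only, and even then it is at most a quarter of a standard error. All of this is correct and limits the size of the point.

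Other objections stand in part:

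- **It is a pilot.** Section 8 promises knowledge of acceptability, feasibility and preliminary impact, and no stated power claim rests on this test. But it is the only test named for stigma, and retention by arm is itself feasibility evidence.
- **Exclusion is inferred.** The plan does not say that incomplete clinicians are dropped. In the long-format fit, the within-clinician stratum is a usable test that draws on anyone with two or more surveys. The remaining difficulty is that the plan does not choose.
- **The evidence of expected loss is general.** The right to skip questions and pro-rated pay are written for Phases 2-4 together, skipping a question is item non-response rather than a missed survey, and surveys are paid. Actual loss may be low.
- **Step 2 decliners add little.** They can supply at most an early score, and the document does not say whether the step 1 survey measures stigma or is one of the three time-points. A mixed model will not recover their follow-up; counting them by arm shows how many there are.

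**Conclusion.** The concern holds as a worthwhile improvement, not a fatal flaw. The plan names a method whose usual form discards incomplete clinicians, foresees incomplete participation, and states no handling for it. At an assumed 10 to 20% missing per follow-up, between 14.8 and 28.1 of 78 clinicians would be excluded. The avoidable increase in standard error is 3 to 6% under monotone dropout and 7 to 15% under independent misses. A completer bias of 0.03 to 0.09 SD is possible if dropout tracks the last score in one arm only, and is about zero if both arms share the mechanism. The attrition rates, correlations and dropout mechanism are all assumptions. If loss is low, or unrelated to stigma, the consequence is a minor loss of precision.

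**What to change.** In section 10, replace the repeated measures ANOVA with a likelihood-based linear mixed model for the three surveys, with condition, time and condition-by-time. REML with unstructured covariance and a small-sample degrees-of-freedom correction would be suitable. State that every randomised clinician with at least one survey is included, in the arm assigned. Report retention by arm at each survey, including the number who decline step 2 consent. Add one sensitivity analysis for departures from missing at random.

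The cost is two or three sentences and slightly more analysis work in R, which the plan already names; no new data items are needed. The drawback is reliance on a missing-at-random assumption, which is why the sensitivity analysis is included. The full benefit also requires that clinicians who leave the training are still sent the surveys. The document does not say whether they are, and it should.

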Phase 4: *Clinicians participating in the intervention pilot will benefit by receiving specialty training in HIV testing, prevention, and linkage to care. We believe that this will be desirable for some because some clinicians volunteer to receive this training via HIV Connect. Additionally, clinicians earn Continuing Medical Education credits after completing each module and assessment of HIV Connect, and a certificate of completion upon finishing all modules and assessments. We will seek approval for the Project ECHO arms to also be eligible for Continuing Medical Education credits, and will amend this protocol to reflect this benefit if our application is approved. Clinicians receive Continuing Medical Education credits for completing Project ECHO in the U.S. and elsewhere.*

Describe any potential future benefits to this class of participants, others, or society.

Clinician stigma remains a potent and persistent driver of disparities in HIV testing, prevention, and linkage to care globally. It is unlikely that we will eliminate these disparities and achieve equity in HIV testing, prevention, and linkage to care until we effectively address clinician stigma. The proposed project will result in important knowledge regarding the acceptability, feasibility, and preliminary impact of a significant and innovative strategy for reducing clinician stigma at large scale: the implementation of evidence-based stigma reduction tools via a popular teletraining platform. In light of the protections that we have in place within our study procedures, we believe that the risks to participants of this project are minimal. We therefore believe that the risks to participants are reasonable in relation to the importance of the knowledge that may be gained from this study.

If there is a Data Monitoring Committee (DMC) in place for this project, please describe when and how often it meets.

N/A

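### The planned condition-by-time ANOVA is valid, but adjusting for stigma measured before assignment would usually give a more precise comparison from the same 78 clinicians

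*Combined protocol and SAP*

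**What the plan says.** Section 10 (DATA), Phase 4, specifies one inferential test for stigma: a "two-way repeated measures ANOVA to determine whether any change in stigma is associated with the interaction between the type of condition (factor one", with time as factor two. The outcome is introduced as follows: "We will examine changes in mean self-reported stigma (i.e., prejudice, stereotypes, and discrimination) across the 3 time-points of data collection". None of the three time-points is labelled baseline, and no covariate is named. The quantitative analyses are also to "include an examination of descriptive statistics and generalized linear models", but no outcome or terms are given for those models.

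Section 7 (STUDY POPULATION AND RECRUITMENT), Phase 4, sets the order of events. At step 1 clinicians "consent to completing a brief survey and being assigned to a study condition". In the random assignment that follows, clinicians' "previous experience with HIV testing will be taken into account in the randomization process to ensure equal distribution of previous experience among study conditions". Then comes step 2: "Once they have been assigned, we will contact them again, provide additional information about their condition, and consent them to the full study". The supplied text does not say whether the step 1 survey contains the stigma items.

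Section 6 (PROCEDURES) gives 26 clinicians in each of three arms. Section 8 (RISKS AND BENEFITS) states the aim: "The proposed project will result in important knowledge regarding the acceptability, feasibility, and preliminary impact" of the strategy.

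**The concern.** If the first survey is baseline, the interaction test treats it as one more response and asks whether the arms changed differently. A change score gives the baseline a fixed weight of one. When baseline and follow-up are imperfectly correlated, that weight is too large and carries baseline noise into the comparison. Adjustment estimates the weight from the data.

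At stake is how much a pilot with 26 per arm can say about preliminary impact. No sample-size rationale is given, so precision per clinician is the main thing the analysis can still improve.

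Two features of the design bear on the choice. Adjustment relies on a baseline that assignment cannot have influenced, and section 7 discloses the condition before full consent. In addition, randomisation takes prior HIV-testing experience into account, but section 10 does not carry that factor into the model.

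**Working it through.** **The plan's own figure.** 3 x 26 = 78, which agrees with section 5 (RESEARCH ABSTRACT). The 78 cannot be derived further, because no alpha, power, effect size or SD is stated.

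**Assumptions.** Two-sided alpha 0.05; SD 1 at each survey; first survey is baseline; no dropout; correlation rho between surveys from 0.3 to 0.9; a 0.5 SD effect in one arm.

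**One follow-up, one pair of arms** (a contrast the plan does not name), n = 26 per arm:

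- Change-score variance: 2(1 - rho) x 2/n
- Baseline-adjusted variance: (1 - rho^2) x 2/n
- Ratio: (1 - rho^2) / [2(1 - rho)] = (1 + rho)/2

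| rho | Ratio | SE, change | SE, adjusted |
|---|---|---|---|
| 0.3 | 0.65 | 0.328 | 0.265 |
| 0.5 | 0.75 | 0.277 | 0.240 |
| 0.7 | 0.85 | 0.215 | 0.198 |
| 0.9 | 0.95 | 0.124 | 0.121 |

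For example, at rho 0.5: sqrt(1.0 x 2/26) = 0.277 and sqrt(0.75 x 2/26) = 0.240.

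**Three arms, three surveys.** This was simulated with 10,000 runs per setting (standard error at most 0.5 points). The planned test is the interaction F on 4 and 150 degrees of freedom: (3-1)(3-1) = 4 and (78-3) x 2 = 150. The adjusted test is the Wilks test of condition on the two later surveys given baseline, F on 4 and 146. With equal correlations, both tests have size between 4.7 and 5.2%. Power, planned / adjusted (%):

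| Effect in one arm | rho 0.3 | rho 0.5 | rho 0.7 | rho 0.9 |
|---|---|---|---|---|
| 0.5 SD at both later surveys | 31 / 54 | 44 / 61 | 68 / 77 | 99.5 / 99.6 |
| 0.25 then 0.5 SD | 25 / 38 | 33 / 43 | 53 / 59 | 97.1 / 97.4 |
| 0.5 SD at last survey only | 33 / 37 | 45 / 48 | 68 / 69 | 99.6 / 99.5 |

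**Decaying correlations** (rho between adjacent surveys, rho^2 between first and last). For the growing effect, planned against adjusted power is 44 against 42% at rho 0.7 and 87 against 79% at rho 0.9. This comparison changes two things at once: it adds baseline, and it replaces a pooled univariate F with a multivariate test. The uncorrected planned F is also slightly oversized here (5.7% and 6.3%). With the form of test held fixed (Wilks on change scores against Wilks given baseline, 1,500 runs per setting), adjustment raises power from about 31 to 41% at rho 0.7 and from about 75 to 78% at rho 0.9.

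**If baseline follows disclosure.** Suppose training has no effect but step 2 uptake leaves one arm 0.3 SD apart at every survey. At rho 0.3, 0.5 and 0.7 the adjusted test then rejects 12.0, 9.3 and 6.8% of the time, and the planned test about 5%. If uptake instead depends on the measured baseline score, the planned test rejects 8.5, 7.3 and 6.0%, and the adjusted test about 5%. Neither test is safe in both cases.

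**The case against.** The strongest reply is that nothing in the plan is wrong. Condition-by-time ANOVA is a standard pre/post analysis, it matches a stated question about change, and this is a pilot with no power target to miss. That stands, and it limits the point to an efficiency gain.

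Four stronger readings are tempting, and the documents do not support them.

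- *The plan ignores baseline.* It does not: with a baseline first survey, the interaction test uses it as a level of time.
- *The plan rules out adjustment.* The generalized linear models have no stated terms, so adjustment there is unspecified, not excluded.
- *Stigma is first measured after disclosure.* The supplied text does not say. Section 15 lists the measures and the two Phase 4 consent forms as separate uploads, which may settle content and timing.
- *Adjustment costs power when correlations decay.* The simulated shortfall comes from changing the form of test, together with a slightly oversized uncorrected F. With the form fixed, adjustment gains.

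It is also fair to object that every rho and effect pattern is assumed and dropout is not modelled. The direction of the variance result does not depend on a particular rho, but its size does. Finally, section 9 (COMPENSATION) pays for up to three hours of Phase 4 surveys. The main instruments may therefore be separate from the brief step 1 survey, and the fix could need more than an edit to the analysis text.

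**Conclusion.** The point holds as a cheap improvement to consider. The planned test is valid but usually less precise than a baseline-adjusted one. The single-contrast variance falls by 35, 25, 15 and 5% at rho 0.3, 0.5, 0.7 and 0.9. For a sustained 0.5 SD effect with equal correlations, power rises by about 23, 17 and 9 points at rho 0.3, 0.5 and 0.7 (54-31, 61-44, 77-68). The gain is smaller for growing effects, only 1 to 4 points for an effect at the last survey alone, and negligible at rho 0.9.

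These sizes rest on assumed correlations, effect patterns and complete data. They also require stigma to be measured before clinicians learn their condition, which the supplied text leaves open.

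**What to change.** In the Phase 4 paragraph of section 10, state that baseline stigma is a measure taken at step 1, before assignment. Then do one of the following:

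- Model stigma at the two later surveys with baseline stigma and the prior HIV-testing experience categories used in randomisation as covariates. Test condition jointly with condition-by-time, because the interaction across the two later surveys alone would miss a constant effect.
- Fit a longitudinal mixed model with a common baseline mean across arms and the same experience categories.

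If stigma is first measured only after disclosure or step 2 consent, randomisation no longer protects the common-baseline assumption. In that case, keep the planned interaction test alongside the adjusted analysis and report both.

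The cost is two or three sentences if the step 1 survey already contains the stigma items. If it does not, they must be added, which changes pre-assignment data collection. The statistical price is a few degrees of freedom out of 78 clinicians and reliance on a baseline taken before disclosure.
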